21.3 Closed formula for sensitivity and specificity of disease biomarkers

Page 44 of 46

The closed formulae in Tilaki-Hajjan *et al*, Journal of Biomedical Informatics 48(2014), 193-2014, were also utilised to understand the power that the samples size above would provide with respect to biomarker sensitivity and specificity.

The following assumptions were made:

- That a sensitivity of 80 % with a precision (d) of between 5-8% would provide a useful biomarker capable of 'ruling out' an acute class. The same target was applied to specificity.
- We assume a prevalence of acute breathlessness of 80% as the MRC EMBER campaign
 uses acute breathlessness as the initial stratification tool for recruitment and 1:5 patients
 recruited will be non-breathless healthy controls. We aim to balance group sizes across
 classes equally.
- A type 1 error rate of 0.05 and power of 95% CI level, 90% CI level
- Note for a prevalence ≥ 50% Nspec ≥ Nsens is always the case, so N_{spec} is the number we need to consider.

95% CI, precision ± 5%

 N_{sens} = 1.96² x 0.8 x 0.2 / 0.05² x 0.8 = 307

 N_{spec} = 1.96² x 0.8 x 0.2 / 0.05² x 0.2 = 1,230

90% CI, precision ± 5%

 N_{sens} = 1.64² x 0.8 x 0.2 / 0.05² x 0.8 = 215

 N_{spec} = 1.64² x 0.8 x 0.2 / 0.05² x 0.2 = 861

To obtain n near 550, increase the maximum marginal error d (i.e. decrease the precision)

95% CI, precision ± 8%, Prevalence = 80%, Sensitivity and Specificity=80 %

 $N_{sens} = 120$

 $N_{\text{spec}} = 480$

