21.4 Summary

550 patients (110 per class: healthy, acute asthma, acute COPD, community acquired pneumonia, acute heart failure) will be required for combined discovery and replication to (i) detect a minimum odds ratio for association of breath VOCs and acute breathlessness of 1.2 or between acute breathlessness class (e.g. pneumonia with remaining categories as a reference).

Page 45 of 46

This sample size and group allocation will give us sufficient power to discover a disease specific VOC over a 95% CI with a specificity of 80% \pm 8%, sensitivity of 80% \pm 8% at an α = 0.05. The sample size will give us sufficient power to replicate based upon biomarker sensitivity but not specificity.

The power calculation assume that ALL acute patients have one or more of the following (i) patient defined acute breathlessness or (ii) a unit change in eMRC (assuming that they can quantify their usual baseline eMRC).

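### Appendix C labels confidence levels as power and claims sufficient power for sensitivity and specificity from a formula that sizes only a confidence-interval half-width

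*Protocol*

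**What the plan says.** Section 21.3 of the protocol introduces closed formulae which, it says, "were also utilised to understand the power that the samples size above would provide with respect to biomarker sensitivity and specificity". Its assumptions include:

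- the target: "That a sensitivity of 80 % with a precision (d) of between 5-8% would provide a useful biomarker", with the same target for specificity;
- the case mix: "We assume a prevalence of acute breathlessness of 80" per cent, the remaining fifth being healthy controls;
- the error rates: "A type 1 error rate of 0.05 and power of 95% CI level, 90% CI level".

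It then works through three settings. A typical line, for specificity at 95% and ± 5%, is "1.96² x 0.8 x 0.2 / 0.05² x 0.2 = 1,230". Since ± 5% needs more patients than planned, the text continues: "To obtain n near 550, increase the maximum marginal error d (i.e. decrease the precision". The last setting is "95% CI, precision ± 8%, Prevalence = 80%, Sensitivity and Specificity=80" per cent, giving 120 for sensitivity and 480 for specificity.

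Section 21.4 turns this into a claim about 550 patients, 110 in each of five classes, over discovery and replication combined: "This sample size and group allocation will give us sufficient power to discover a disease specific VOC over a 95% CI with a specificity of". The target named there, for both measures, is 80% with a margin of 8 points either way, at α = 0.05. It adds that power is sufficient to replicate on sensitivity but not on specificity. It gives no power value for either statement.

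**The concern.** Power is the probability that a stated test succeeds under a stated truth. It needs a value to be excluded, an assumed true value and a 1−β. Section 21.3 supplies a true value (80%) and a confidence level, and calls the confidence level power. Section 21.4 carries that label into its conclusion.

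Sensitivity and specificity belong to the primary objective (section 5.1), and sections 21.3 and 21.4 are the only places where the protocol says whether the sample is adequate for them. The only power value in Appendix C, 80%, belongs to the odds-ratio calculation in section 21.2. Because 21.4 reports the odds-ratio and accuracy claims together and then refers to the power calculation as one thing, a reader may carry the 80% across to the accuracy claim, where nothing supports it. Section 10.2 says the study will serve as a basis for sizing a larger one, so the mislabel could be carried forward.

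**Working it through.** **Inputs, all from sections 21.3 and 21.4.** p = 0.80 for sensitivity and specificity; d = 0.05 or 0.08; prevalence 0.80, so 0.20 healthy; z = 1.96 (95%) or 1.64 (90%); 550 patients in five classes of 110. Section 21.5 splits each class 55 and 55 between phases.

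**Step 1. Reproduce the stated sample sizes.** N_sens = z²·p(1−p)/(d²·0.8) and N_spec = z²·p(1−p)/(d²·0.2), with p(1−p) = 0.16.

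| Setting | N_sens computed (stated) | N_spec computed (stated) |
|---|---|---|
| 95%, ± 5% | 307.3 (307) | 1,229.3 (1,230) |
| 90%, ± 5% | 215.2 (215) | 860.7 (861) |
| 95%, ± 8% | 120.05 (120) | 480.2 (480) |

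All six agree to rounding. The only z is the one for the confidence level; no z for power enters any line.

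**Step 2. What the planned numbers deliver.** Expected 95% half-width = 1.96·√(0.16/n).

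| n | Who this could be | Half-width |
|---|---|---|
| 110 | all healthy controls, or one disease class | 7.5 points |
| 440 | all acute patients, or the four classes other than the target | 3.7 points |
| 55 | one class or the controls, one phase | 10.6 points |
| 220 | all acute patients, one phase | 5.3 points |

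Read as precision, ± 8 holds for both measures at the pooled size. In a single phase it does not hold for the measure that rests on 55 participants.

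**Step 3. Which measure rests on which number.** For acute versus healthy, sensitivity rests on 440 and specificity on 110. For one class against the rest, which the phrase about a disease-specific VOC suggests, sensitivity rests on 110 and specificity on 440. If the reference is the other acute classes only (section 21.2), specificity rests on 330, and 1.96·√(0.16/330) = 4.3 points.

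**Step 4. Illustration only: what a power statement would look like.** Assume the aim were a lower 95% limit above 72% when the truth is 80%. The protocol does not state this aim. By normal approximation with variance at 0.80, power = Φ(0.08/√(0.16/n) − 1.96).

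- n = 110: Φ(2.098 − 1.96) = 55%. Exact binomial: 56% (Wald limits), 46% (Wilson), 46% (Clopper-Pearson).
- n = 440: Φ(4.195 − 1.96) = 99%. Exact binomial: 98%, 97% and 97%.

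The ranges are therefore about 46–56% with 110 and about 97–99% with 440.

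**The case against.** The strongest reply is that the calculation is openly one of precision. Section 21.3 calls d a precision and a marginal error, heads every setting with a confidence level and a ± figure, and section 21.4 repeats the ± 8%. On that reading the numbers are right and the pooled half-widths are within 8 points. Nor did this calculation set the sample size: 21.3 describes a size already reached from the odds ratio with 80% power in 21.2, and section 10.2 cites a 20:1 ratio of events to variables and calls the study exploratory. All of this stands. It limits the point to what is claimed and leaves the design untouched. It does not rescue the word power, which is in the assumptions, in the stated purpose of the formulae and in both conclusions of 21.4.

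A reader might infer more: that the study has only a coin-toss chance of success, or that specificity is underpowered. The documents do not support that. They name no test against 72%, no minimum acceptable value and no decision rule on a lower limit. A chance of about one half of excluding the margin is what the normal approximation gives for any half-width formula at its own N. With 440 participants the illustrative power is 97–99%. Which measure has only 110 reverses with the contrast chosen in step 3.

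**Conclusion.** The point holds as a mislabelled and unsupported claim. Section 21.3 gives confidence levels as power, and both statements of sufficient power in section 21.4 rest on a formula without a power term. The six sample sizes are correct as precision figures. No power for sensitivity or specificity has been calculated, so the protocol can call it neither sufficient nor insufficient.

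What the plan does support is an expected 95% half-width of about 7.5 points on the measure that rests on 110 participants and 3.7 on the one that rests on 440, with both phases pooled. These figures assume a true value of 80%, equal classes as planned and simple binomial variance. The power figures of 46–56% and 97–99% also assume a 72% threshold that the protocol does not set, so they should not be cited as the power of this study.

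**What to change.** In section 21.3, replace power in the error-rate assumption with a confidence level of 95% or 90%, and say that the formulae show the precision the sample provides.

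In section 21.4, replace both statements of sufficient power with the expected 95% half-widths at a true value of 80% for the numbers actually used: about ±7.5 points with 110, ±3.7 with 440, ±10.6 with 55 in one phase and ±5.3 with 220 in one phase. State whether the contrast is acute versus healthy or one class versus the rest, since this decides which figure belongs to sensitivity and which to specificity.

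If a power statement is to be kept, name the value to be excluded, the assumed true value and the interval method, and calculate the power from those.

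The cost is the rewording of a few sentences and a less favourable stated claim. No more patients are needed.

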21.4 Summary

550 patients (110 per class: healthy, acute asthma, acute COPD, community acquired pneumonia, acute heart failure) will be required for combined discovery and replication to (i) detect a minimum odds ratio for association of breath VOCs and acute breathlessness of 1.2 or between acute breathlessness class (e.g. pneumonia with remaining categories as a reference).

Page 45 of 46

This sample size and group allocation will give us sufficient power to discover a disease specific VOC over a 95% CI with a specificity of 80% \pm 8%, sensitivity of 80% \pm 8% at an α = 0.05. The sample size will give us sufficient power to replicate based upon biomarker sensitivity but not specificity.

The power calculation assume that ALL acute patients have one or more of the following (i) patient defined acute breathlessness or (ii) a unit change in eMRC (assuming that they can quantify their usual baseline eMRC).

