21.2 Closed formula for logistics regression models

82 acutely breathless adults (asthma:35, community acquired pneumonia :16, COPD:26) and 17 healthy controls were utilised for the analysis.

A panel of 10 pre specified aldehyde biomarkers derived from GCMS analysis were supplied. The biomarkers were normalised to a common standard and were not background subtracted.

A closed formula from Hsieh et al, Statis med 1998, was utilised to calculate sample sizes from logistic regression models of the 10 aldehydes with acute breathlessness as the outcome measure. The sample size estimates are also relevant to acute class comparions vs. the sum of other acute classes.

The results of the analyses are outlined in the figure below (each BRI number annotates a specific aldehyde).

Based upon the sample size estimates we would have an 80% power at the 5 % significance level to detect an odds ratio of association of 1.2 for a given disease class with 55 patients per disease class. Given the fact that MRC EMBER seeks to discover and replicate breath VOCs amongst 5 adults classes (CAP, heart failure, COPD, asthma and healthy aged matched subjects).

We would require 110 patients per class – 550 patients across the program to achieve these aims.

Commented [CSB1]: This is not a complete sentence. There is a clause missing, or else the punctuation needs adjustment.

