21.5 Recruitment Plan: Acute Adult Study

Disease Category	Discovery	Replication
Acute Adult Asthma	55	55
Acute COPD	55	55
Acute Heart Failure	55	55
Community Acquired	55	55
Pneumonia		
Adult healthy volunteers	55	55

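### Section 21.4 claims specificity of 80% ± 8% for discovery, but the 55 discovery controls in section 21.5 give ± 10.6%, the same as in the replication phase it calls inadequate

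*Protocol*

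**What the plan says.** Section 21.2 finds 55 patients per class sufficient for the odds-ratio target. It doubles this to 110 per class because the programme must both discover and replicate, giving "550 patients across the program to achieve these aims".

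Section 21.3 then considers precision. It takes a target of 80% for both sensitivity and specificity, and a case fraction of 80% ("We assume a prevalence of acute breathlessness of 80% as the MRC EMBER campaign"), with healthy controls as the non-cases. It notes that the specificity total is the one that governs. The ± 5% target needs more than 550, so the margin is widened: "To obtain n near 550, increase the maximum marginal error d (i.e. decrease the precision"). At ± 8% with a 95% interval it obtains totals of 120 for sensitivity and 480 for specificity.

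Section 21.4 states that 550 is the number for discovery and replication combined. It then says that this size and allocation "will give us sufficient power to discover a disease specific VOC over a 95% CI with a specificity of 80"% ± 8%, with sensitivity likewise 80% ± 8%. The next sentence reads: "The sample size will give us sufficient power to replicate based upon biomarker sensitivity but not specificity".

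Section 21.5 allocates 55 to each of five classes in each phase, including 55 in the row "Adult healthy volunteers" for discovery and 55 for replication. The synopsis and sections 5.1 and 7.1 give a wider range of 55-150 adult controls in discovery. The replication range is 55-75.

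**The concern.** Section 21.4 makes different claims for two phases that section 21.5 makes the same size with the same allocation. Precision depends on the number of controls, so if specificity is inadequate in replication it is equally inadequate in discovery. The phrase 'sample size' appears to change meaning between consecutive sentences: the discovery claim is true at 550 and the replication claim at 275.

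The primary objective (section 5.1) is to estimate sensitivity, specificity and predictive values, and section 21.4 is where the protocol summarises the precision to expect. A reader deciding how many controls to enrol within 55-150 would conclude that 55 is enough for specificity within 72% to 88%. Reaching ± 8% by pooling instead would use the replication controls for discovery, although section 7.1 describes two distinct phases.

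**Working it through.** **Inputs.** From section 21.3: target p = 0.8 for sensitivity and specificity, so p(1 − p) = 0.16; z = 1.96; d = 0.08; case fraction 0.8. From section 21.5: 55 per class per phase, so each phase has 4 × 55 = 220 acute adults and 55 controls, 275 in all.

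**Reproducing section 21.3.** With N_sens = z²·p(1 − p)/(d²·prev) and N_spec = z²·p(1 − p)/(d²·(1 − prev)):

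- d = 0.05, z = 1.96: 307.3 and 1,229.3 (stated 307 and 1,230).
- d = 0.05, z = 1.64: 215.2 and 860.7 (stated 215 and 861).
- d = 0.08, z = 1.96: 120.05 and 480.2 (stated 120 and 480).

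The arithmetic in section 21.3 is sound.

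**Controls needed for ± 8%.** 1.96² × 0.16/0.08² = 96.04, so 97 after rounding up. This is the 480 × 0.2 = 96 implied by section 21.3. It does not depend on the case fraction.

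**Totals against requirements.** Pooled: 550 exceeds both 120 and 480. One phase: 275 exceeds 120 but falls short of 480. One phase therefore supports sensitivity but not specificity, which is what section 21.4 says of replication only.

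**Half-width, 1.96 × √(0.16/n), at a true value of 80%:**

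| Group | n | 95% half-width |
|---|---|---|
| Controls, either phase (21.5) | 55 | ± 10.6% |
| Upper replication control figure | 75 | ± 9.1% |
| Controls at which ± 8% is met | 97 | ± 7.96% |
| Controls, phases pooled | 110 | ± 7.5% |
| Upper discovery control figure | 150 | ± 6.4% |
| Acute adults, either phase (21.5) | 220 | ± 5.3% |

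The interval with 55 controls is 80 ± 10.57, or 69.4% to 90.6%. Putting d = 0.1057 back into the N_spec formula at 80% prevalence returns 275, the section 21.5 total for one phase.

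**Other interval methods at 55 controls (44/55).** Wilson gives 67.6% to 88.4% (half-width 10.4%) and Clopper-Pearson 67.0% to 89.6%. A 90% normal interval gives ± 8.9%. None reaches ± 8%.

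**One class against the rest.** Section 21.4 speaks of a disease-specific marker and gives the example "pneumonia with remaining categories as a reference", while section 21.2 says: "The sample size estimates are also relevant to acute class comparions vs. the sum of other acute classes". The 80% case fraction in section 21.3 fits neither.

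- Healthy included in the reference: case fraction 55/275 = 20%, so N_sens = 480 and N_spec = 120.
- Other acute classes only: case fraction 55/220 = 25%, so N_sens = 384 and N_spec = 128.

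On both readings sensitivity governs. For a class of 55 it is ± 10.6%; at the upper recruitment figure of 100 it is ± 7.8%; for asthma and COPD combined (110) it is ± 7.5%.

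**The case against.** **The sentence may refer to all 550.** The only size and allocation stated before it is 550 at 110 per class, and 480 is below 550. Read that way the figure is correct. But discovery would then use every participant, against the equal split in section 21.5, the two distinct phases in section 7.1 and the separate replication claim in the next sentence. At best the claim lacks the condition that makes it true.

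**The recruitment ranges favour the asymmetry.** Discovery may enrol up to 150 adult controls and so can reach ± 8%. Replication is limited to 75 (± 9.1%) and cannot. This stands as a description of the ranges, and it means that equality between phases holds only at the section 21.5 allocation. It does not rescue section 21.4, which rests its claim on 110 per class; the discovery range also starts at 55.

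**One class against the rest.** On that reading discovery specificity rests on 220 non-cases (± 5.3%), or 165 if only the other acute classes are used (± 6.1%), so specificity meets ± 8%. This is correct, but the joint claim then fails on sensitivity, at ± 10.6% for 55 cases, and the remark that replication is adequate for sensitivity but not specificity would be reversed for a single class.

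**Consequences are limited.** Section 10.2 calls the study exploratory, no decision rule uses ± 8%, section 10.6 provides for recalculating the replication numbers, and the primary model in section 10.1 compares acute with recovery, which these half-widths do not describe. All of this stands and limits the weight of the point. It does not make the stated precision correct.

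**Conclusion.** The concern holds. At the section 21.5 allocation, discovery specificity for acute versus healthy is known to ± 10.6%, not ± 8%: the half-width is about a third larger than stated (10.57/8 = 1.32). Replication has the same precision. The sensitivity part of the claim holds in each phase for acute versus healthy (± 5.3%). A specificity of ± 8% is available only from the pooled phases or from about 97 or more discovery controls.

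These figures assume a true value of 80%, the normal-approximation formula of section 21.3 and healthy controls as the non-cases. 'Power' in section 21.4 means interval width, since section 21.3 contains no hypothesis test. The unclear reference group is a secondary point; the main finding does not depend on it. The text should be corrected.

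**What to change.** Restate section 21.4 by phase:

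- Give specificity of ± 10.6% with 55 controls and sensitivity of ± 5.3% with 220 acute adults, for each phase.
- Attach ± 8% specificity either to the pooled 550 or to a stated condition of about 97 or more discovery controls within the 55-150 range.
- Name the reference group for a disease-specific marker and give the matching totals: N_sens 480 and N_spec 120 if healthy volunteers are included, or N_sens 384 and N_spec 128 if only the other acute classes are used.
- Limit the statement that replication is adequate on sensitivity to acute versus healthy and to asthma and COPD combined, and give ± 10.6% for a single class of 55.
- Note that the replication numbers are planning minima pending the recalculation in section 10.6.

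The change is confined to the wording of Appendix C. The stated discovery precision becomes less favourable, and no extra patients are needed.

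### Section 21.4 applies sample sizes derived for acute breathlessness (80% prevalence) to a single-disease marker, for which the replication statement is reversed at 55 per class

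*Protocol*

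**What the plan says.** Protocol, Appendix C, section 21.3 sets its requirement in terms of a class: "That a sensitivity of 80 % with a precision (d) of between 5-8% would provide a useful biomarker capable of 'ruling out' an acute class". It adds: "The same target was applied to specificity". The prevalence it then uses is that of the whole acute group: "We assume a prevalence of acute breathlessness of 80" per cent, because one recruit in five is a healthy control. On allocation it says: "We aim to balance group sizes across classes equally". It names the governing requirement on the strength of that prevalence: "Note for a prevalence ≥ 50% Nspec ≥ Nsens is always the case". For a 95% interval of ±8% it reports N_sens = 120 and N_spec = 480.

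Section 21.4 fixes 550 adults, 110 in each of five classes, across discovery and replication together. It says this size "will give us sufficient power to discover a disease specific VOC over a 95% CI" with sensitivity and specificity each at 80% ± 8%. The next sentence is: "The sample size will give us sufficient power to replicate based upon biomarker sensitivity but not specificity".

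Section 21.5 plans 55 per class in each phase.

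**The concern.** The calculation and the claim concern different targets. In 21.3 a case is any acutely breathless adult, four classes out of five. In 21.4 the marker is specific to one disease. The paragraph just before that claim gives pneumonia against the remaining categories as its example, and a secondary objective in section 5.2 is to discover and replicate markers that separate heart failure, pneumonia and asthma/COPD.

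For one class the case fraction is 1 in 5, or 1 in 4 if only acute adults are compared. The condition that made N_spec the governing number (prevalence of at least 50%) then fails, and N_sens governs.

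What is at stake is how a replicated class marker will be read. The protocol wants a marker that can rule out a class, which depends on sensitivity. A reader of 21.4 would take sensitivity to be the measure that replication estimates well. For a single class at the planned minimum it is the less precise one.

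**Working it through.** **Inputs.** Sensitivity and specificity 80%, z = 1.96, d = 0.08 and prevalence P = 0.80 (section 21.3). Five equal classes, 55 per class per phase (section 21.5). One phase therefore has 5 × 55 = 275 adults, and both phases have 550.

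**Formulas.** N_sens = z² × 0.8 × 0.2 / (d² × P). N_spec = z² × 0.8 × 0.2 / (d² × (1 − P)). The half-width for n subjects in the relevant group is 1.96 × √(0.16 / n).

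**Reproducing the plan.** The common factor is 1.96² × 0.16 / 0.08² = 96.04, which is the number needed in the relevant group itself. At P = 0.80:
- N_sens = 96.04 / 0.80 = 120.05
- N_spec = 96.04 / 0.20 = 480.2

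These match the stated 120 and 480. The ±5% figures in 21.3 also reproduce: 307.3 and 1,229.3 at z = 1.96, 215.2 and 860.7 at z = 1.64. The replication sentence follows from this target, since 275 exceeds 120 but not 480.

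**One class against the rest.**
- Against all others, P = 0.20: N_sens = 96.04 / 0.20 = 480 and N_spec = 96.04 / 0.80 = 120.
- Against the other acute classes only, P = 0.25: N_sens = 96.04 / 0.25 = 384 and N_spec = 96.04 / 0.75 = 128.

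A phase of 275 now exceeds the specificity requirement (120) but not the sensitivity requirement (480). Among acute adults only, 4 × 55 = 220 exceeds 128 but not 384.

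**Half-widths in percentage points.**

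| Target | Cases / non-cases | Sensitivity | Specificity |
|---|---|---|---|
| Acute v healthy, one phase | 220 / 55 | ±5.3 | ±10.6 |
| One class v all others, one phase | 55 / 220 | ±10.6 | ±5.3 |
| One class v other acute, one phase | 55 / 165 | ±10.6 | ±6.1 |
| One class v all others, both phases | 110 / 440 | ±7.5 | ±3.7 |

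**Where the reversal stops.** Sensitivity reaches ±8 with about 96 cases of the class in a phase. Sections 5.1 and 5.2 plan 55–100 per phase for heart failure and for pneumonia; 100 cases give ±7.8. Asthma and COPD combined are planned at 110–200 per phase; 110 cases give ±7.5.

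**The case against.** The strongest defence is that the disputed sentence says only biomarker sensitivity and names no class. Section 21.3 states openly that its prevalence is that of acute breathlessness, and this is the condition in the primary objective. The closing paragraph of 21.4 also describes the calculation in terms of acutely breathless patients. Read that way, the sentence is correct. This stands, and it means the sentence must not simply be inverted or deleted: replicating the breathlessness markers is itself a secondary objective in section 5.2. It does not rescue the text as written, because the sentence directly before it is about a disease-specific marker and nothing signals a change of target.

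A second defence is that the ±8% claim is numerically true for a class marker if it refers to the 550 named just above it (±7.5 and ±3.7). This also stands. A reader might infer that the claim is false in every reading. It fails, for sensitivity, in a single phase with fewer than about 96 cases of the class.

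A third defence is that little depends on the passage. The 55 per class comes from the logistic-regression calculation in section 21.2; section 21.3 was added to see what precision that size would give. Section 10.2 calls the study exploratory, and section 10.6 plans a further calculation of the size of each replication group. A reader might infer that the study is undersized or that recruitment must change. The documents do not support that inference. The defence bears on the weight of the point and leaves the wording unresolved.

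**Conclusion.** The concern holds as a mismatch between the target calculated and the target named. At the planned minimum of 55 per class per phase, a marker for one class has a sensitivity half-width of ±10.6 points, so an observed 80% carries an interval of about 69% to 91%. That is outside the protocol's own 5–8% limit. Specificity is ±5.3, or ±6.1 against the other acute patients. The replication statement is thus right for acute breathlessness against healthy and reversed for a single-class marker.

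This rests on equal classes, a true value of 80% for both measures, the plan's own normal-approximation formula, and replication being judged on its own phase. It no longer applies at about 96 or more cases of the class in a phase.

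A reader might take this as an arithmetic error, but every figure checked in 21.3 reproduces. It is a moderate correction to a precision statement, because the recruitment numbers do not depend on it.

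**What to change.** In sections 21.3 and 21.4, name the target of each statement and report both. Possible wording for the replication statement:

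> For acute breathlessness v healthy, a replication phase with 55 per class gives sensitivity 80% ± 5.3% and specificity 80% ± 10.6%. For a single-class VOC v the rest, it gives sensitivity 80% ± 10.6% and specificity 80% ± 5.3%; ± 8% for sensitivity needs about 96 cases of that class.

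In 21.3, limit the remark that N_spec governs to the acute-v-healthy target, and add the class-marker requirements at ±8%: N_sens 480 and N_spec 120 (384 and 128 among acute adults only). In 21.4, say that the ±8% discovery claim for a disease-specific VOC refers to the pooled 550, since discovery alone at 55 per class does not reach it for sensitivity.

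The cost is text in Appendix C and a less favourable stated precision for class markers in a single phase. It needs no extra patients or procedures.
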